## 6. Statistical Analyses.

**6.1. Statistical Analysis Plan.** Descriptive statistics will be used to summarize quantitative feasibility outcomes with numbers and rates. Benchmarks for success of the telehealth MBI will be: 1) enrollment rate of at least 50% of eligible patients; 2) 90% of sessions attended on average; 3) 80% of home practice completed on average; 4) intervention retention of at least 90%; 5) moderate to high intervention satisfaction rated by at least 80% of participants.

Transcription of interview data will be verified prior to analysis. The PI and study personnel will conduct line by line analysis using Dedoose analytic software. Themes and textual examples will be independently identified and subsequently discussed for consensus. Analysis will be an ongoing, iterative process following each 2 to 4 interviews to ensure that data saturation ultimately occurs before discontinuing interviews. A codebook will be generated by isolating individual quotes and refined as additional interviews are coded. Thematic analysis of codes will be used to identify emergent themes, or patterns of meaning, found in the data with regards to participant experiences with the telehealth MBI and specific post-surgical concerns. Quantitative and qualitative data results will be merged to identify aspects of the telehealth MBI that need to be adapted to optimize acceptability for post-surgical patients.

Within-group, within-subject changes from baseline to the follow-up post-intervention assessment in pain-related outcomes, opioid use, and psychosocial characteristics will be explored by examining change in scores and their respective standard errors with 95% confidence intervals.

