**Protocol**

# Post-op Telehealth Mindfulness Protocol for Spinal Surgery

## Design Synopsis

**Title:** Optimizing a Postoperative Telehealth Mindfulness Intervention to Improve Pain-related Outcomes and Reduce Opioid Use After Spine Surgery

**Principal Investigator:** [name]

**Participating Center:** Vanderbilt University Medical Center

**Sponsors:** Osher Center for Integrative Medicine at Vanderbilt (7/1/20 - 6/30/21); NIH - National Center for Complementary and Integrative Health (8/5/21 - 7/31/26)

**Type of study:** Two-arm intervention development and feasibility pilot trial

**Objective:** The overall objectives of our preliminary, mixed-methods project are to optimize a mindfulness-based intervention (MBI) for patients recovering from lumbar spine surgery to improve pain-related outcomes and reduce post-surgical opioid use, and to evaluate its feasibility and acceptability. We will pilot an existing, group-based MBI for chronic pain patients that we have formatted for both one-on-one and group telehealth delivery to postsurgical patients, and utilize participant feedback to tailor the intervention to post-surgical orthopaedic patients.

**Specific Aim 1: To evaluate the feasibility and acceptability of the telehealth MBI.** We will conduct a nonrandomized, sequential pilot test of the individual telehealth MBI (approximately 16 completers) and of the group telehealth MBI (approximately 8 completers) with patients recovering from lumbar spine surgery. We anticipate enrolling up to 34 participants to have 24 complete the study. Feasibility and acceptability of the individual and group intervention will be evaluated as recruitment rates, session attendance, home practice assignment, study retention, and participant satisfaction.

**Hypothesis 1:** a) Participants will be recruited at a rate of 50%; b) Participants will attend 90% of sessions on average; c) Participants will complete 80% of home practice assigned; d) Study retention will be 90% at post-intervention; e) 80% of participants will report moderate to high satisfaction with the intervention.

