## Post-op Telehealth Mindfulness Protocol for Spinal Surgery

- 5) Radiographic evidence of a degenerative condition including but not limited to *spinal stenosis, spondylosis with or without myelopathy, and spondylolisthesis*
- 6) Presence of back and/or lower extremity pain persisting for at least 3 months
- 7) Access to stable internet.
- 8) Able to participate in weekly, remote sessions with a study therapist for 8 weeks after surgery

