## **5. Trial Protocol**

**5.1. Overview.** The patient-related activities of the postoperative telehealth mindfulness trial can be divided into the following phases.

- Phase 1: Consent into study and screening for eligibility
- Phase 2: Enrollment into trial prior to surgery, preoperative data collection
- Phase 3: Postoperative Baseline data collection (2 weeks after surgery)
- Phase 4: Intervention (8 weeks)
- Phase 5: Post-intervention data collection and semi-structured interviews (3 months after surgery)

**5.2. Phase 1: Consent into Study and Screening for Eligibility.** Patients will be approached for their consent to participate in the study following their preoperative clinic visit either at the clinic as available or over the phone, with the permission of the treating surgeon. If over the phone, participants will sign an e-consent form through a REDCap survey link. The study coordinator will perform the consent process using a scripted dialogue and materials developed for the study.

Patients will then be screened for eligibility in the surgical center or over the phone by the research coordinator. Screening through the medical record will occur prior to surgery and a scheduled preoperative clinic visit. Additional screening will occur either immediately after the preoperative clinic visit at the Spine Center or after the visit over the phone by the study coordinator through a list of screening questions. All potentially eligible patients will be entered into REDCap, a study number assigned, and eligibility criteria confirmed.

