## Post-op Telehealth Mindfulness Protocol for Spinal Surgery

**5.3. Phase 2: Enrollment and Preoperative Data Collection.** Once consented into the study and determined to be eligible, patients will complete a preoperative questionnaire using a REDCap survey either at the clinic after the visit, online after the visit, or over the phone after the visit if preferred. This self-report assessment will gather data on patient demographic and injury characteristics, medical and social history, pain self-efficacy, negative affect, dispositional mindfulness, concerns about pain, current opioid use and preoperative levels of pain and disability. Opioid prescription and dosages will also be extracted from the electronic medical record.

**5.4. Phase 3: Baseline Data Collection (2 weeks after surgery).** Study participants who complete surgery will be emailed or texted (based on participant preference) a REDCap survey to collect baseline data at two-weeks after surgery. They can also complete the survey at the postoperative clinic visit or over the phone. Similar to the pre-operative questionnaire, this self-report assessment will gather data on pain self-efficacy, negative affect, dispositional mindfulness, concerns about pain, current opioid use and levels of pain and disability. Opioid prescription and dosages will also be extracted from the electronic medical record.

At this time, participants will also meet with the research coordinator, either at their post-operative clinic visit or by phone, to become oriented to the telehealth platform that will be used during intervention sessions. If the participant does not have their own device for use during the intervention, they will be provided with a tablet by the research coordinator.

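### Is the 50% enrolment benchmark empty because the plan does not say how patients who decline before the screening questions are counted?

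*Combined protocol and SAP*

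**What the plan says.** Enrolment heads the list of primary feasibility outcomes (Design Synopsis and section 5.7). Section 6.1 makes it the first of five benchmarks: an "enrollment rate of at least 50% of eligible patients". Hypothesis 1a sets the same target without a denominator: "Participants will be recruited at a rate of 50" per cent. Section 6.1 promises descriptive summaries giving counts as well as rates.

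The recruitment steps are in sections 5.1 to 5.3:

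- The phase list reads "Phase 1: Consent into study and screening for eligibility".
- After the paragraph on consent, section 5.2 continues: "Patients will then be screened for eligibility in the surgical center or over the phone by the research coordinator".
- The same paragraph adds: "Screening through the medical record will occur prior to surgery and a scheduled preoperative clinic visit". Sections 5.2 and 7.3 place the consent approach after that visit.
- Section 5.2 closes: "All potentially eligible patients will be entered into REDCap, a study number assigned, and eligibility criteria confirmed".
- Section 5.3 starts preoperative data collection "Once consented into the study and determined to be eligible".

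Two other places bear on the word eligible. The sample-size entry of the Design Synopsis has up to 34 eligible patients giving consent. Section 4.1 has eligible patients being identified and then recruited.

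**The concern.** On a literal reading of section 5.2, the screening questions follow consent. Some inclusion criteria, such as "Access to stable internet" or being able to attend weekly remote sessions, are unlikely to be settled from a medical record. A patient who passes the record screen and then declines is therefore of unknown eligibility. If only patients with every criterion confirmed count as eligible, the numerator and denominator are almost the same people. The benchmark then could hardly be missed and would say nothing about uptake. If eligible means having passed the record screen and been approached, it can be missed. Since enrolment is a primary outcome with a stated success threshold, the same recruitment data could be reported as a clear success or a clear failure.

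**Working it through.** **The plan's own figure.** The 50% is a set target, not a derived quantity, so there is no calculation to reproduce. With 34 patients enrolled, a 50% rate implies 34/0.5 = 68 eligible patients.

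**How far the readings can diverge.** The documents give no consent or screen-failure rate, so both are assumed. Let c be the share of approached patients who consent, and f the share of consenters found ineligible by the questions.

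- Confirmed-eligible reading: c(1−f)/[c(1−f)] = 100% for any c above zero, if no one is lost between confirmation and enrolment. If enrolment means completing the preoperative questionnaire and 1, 2 or 3 of 34 are lost first, the rate is 97.1%, 94.1% or 91.2%.
- Approached reading, with decliners kept and ineligible consenters removed: c(1−f)/(1−cf).

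| c | f | Confirmed reading | Approached reading |
|---|---|---|---|
| 20% | 10% | 100% | 0.18/0.98 = 18.4% |
| 30% | 10% | 100% | 0.27/0.97 = 27.8% |
| 40% | 10% | 100% | 0.36/0.96 = 37.5% |

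The approached reading reaches 50% when c = 0.5/(1−0.5f), that is 50.0%, 52.6%, 55.6% or 58.8% for f = 0, 10%, 20% or 30%. Below that consent share the two readings disagree on the benchmark; at or above it both pass. Nothing in the documents indicates on which side the trial will fall.

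**Which reading the text supports.**

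- Section 6.1 says eligible. The restriction to patients confirmed after consent has to be added by the reader.
- The Design Synopsis and section 4.1 both treat eligible patients as a group from which people are then consented or recruited.
- The record screen comes before the preoperative visit and the approach comes after it, so a screened group exists before anyone can decline.
- The REDCap entry covers potentially eligible patients and is not restricted in words to consenters, although it does not expressly include decliners either.
- A 50% target has no purpose under a definition that returns 100% by construction.

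**Would one prescribed denominator be better?** Take the approached reading as the rule, with c = 55%, f = 20%, and the same 20% ineligible among decliners. Of 100 approached:

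- 55 consent, 11 of them are ineligible, and 44 enrol.
- 45 decline, of whom 9 are ineligible and 36 eligible.
- True uptake among eligible patients: 44/(44+36) = 55%, which meets the benchmark.
- The rule: 44/(44+45) = 49.4%, which misses it.

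Under equal ineligibility, the rule gives a false miss whenever c is at least 50% but below 55.6% (f = 20%) or 58.8% (f = 30%). The error here is 55 − 49.4 = 5.6 percentage points. For comparison, the 95% sampling half-width at 34 of 68 is 1.96 × √(0.5 × 0.5/68) = 11.9 points.

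**The case for a change.** The strongest case for a change is that the gap is real and cheap to close. No section names the denominator, Hypothesis 1a is silent, and reporting counts helps only if decliners are among them. A decliner not tallied during accrual may not be recoverable later. How decliners of unknown eligibility are treated can also decide the result. With 34 enrolled and 51 decliners (assumed), the rate is 34/34 = 100% if they are left out. It is 34/59.5 = 57.1%, 34/69.7 = 48.8% or 34/79.9 = 42.6% if 50%, 70% or 90% of them are eligible. A sentence or two in section 6.1 would settle this without touching eligibility, procedures or sample size. The sequence in section 5.2 does lend some support to the confirmed reading, and the Design Synopsis and section 4.1 do not say how eligibility is established in someone who declines.

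What stands is that the plan leaves a detail unstated and that the counts approached, declined, found ineligible and enrolled should accompany the rate. What does not stand is that the benchmark as written is automatically met. The 100% comes only from adding a word to section 6.1 and setting aside the two places that put eligibility before consent. The remaining spread, from 57.1% to 42.6%, reflects not knowing how many decliners were eligible. Naming a denominator does not remove that uncertainty; displayed counts let a reader see it.

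**Conclusion.** No change to the plan is needed. This is a missing detail that an analyst would fill sensibly by dividing enrolled patients by eligible patients approached and giving the counts. The large contrast, 100% against figures such as 27.8%, depends on a reading that would make the 50% target pointless and that the Design Synopsis and section 4.1 contradict. Between sensible denominators the difference is smaller: 5.6 points in the worked case, within the 11.9-point sampling half-width at 68 patients. The obvious single rule can itself reverse the result. The benchmark is one of five descriptive ones in a nonrandomized feasibility pilot, and no test, sample size or stated progression rule depends on it.

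The size of the effect rests on assumed consent, screen-failure and decliner-eligibility rates, since the documents give none. The conclusion rests on decliners being tallied during accrual, which the plan neither requires nor rules out.

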## 7. Human Subjects Issues

**7.1. Sources of Materials.** All materials will be collected and recorded for research purposes. The socio-demographic, clinical, and outcomes information collected during this investigation will be obtained from multiple sources, including subjects directly, medical records, and hospital databases. These data will be entered directly into REDCap (a secure, web-based application). All data will be secured by password-only access for the purpose of confidentiality. The surgery and clinic notes will also be used to collect data. Outcomes data will be derived from questionnaires completed both in the clinic and online remotely, and through interactions between the patient and research personnel during semi-structured phone interviews.

**7.2. Potential Risks.** The risk to human subjects of participation in this study is minimal due to the nature of this behavioral treatment. The possibility exists that a participant may experience a degree of emotional discomfort related to intervention activities resulting in increased awareness of unpleasant experiences, or emotional distress due to completing questionnaires about mood and pain-beliefs. Research personnel and study interventionists will have referral sources available for individuals who request or are in need of further counseling or support. Study interventionists will be post-doctoral level psychologists with training in responding to potential increase in distress during the study, as well as

## Post-op Telehealth Mindfulness Protocol for Spinal Surgery

responding to reports of severe depression, suicidal ideation, or other medical/psychological problem requiring additional attention. If this should occur, the PI and referring surgeon will be notified and appropriate referrals arranged. There is a small risk of breach of confidentiality, but the data for this study will be secured in a password protected database. Access to this database will be limited to the investigators and study staff. Data will be deidentified for data analysis and interpretation.

**7.3. Recruitment and Informed Consent.** Prototype consent will be prepared for the trial. Before approaching patients for enrollment prior to surgery, discussions will be conducted with patients' surgeons to obtain permission. The surgeon and clinical staff will be fully informed of the nature of the study and any risks and benefits. The research coordinator will approach the patient after the preoperative clinic visit or a preoperative education class. The coordinator will meet with the patient, as well as family members if requested by patient, and will describe the proposed study protocol using a scripted dialogue and materials developed for the study. It will be emphasized to all study participants and family members that the data collected will be for research purposes and that refusal to participate in the investigation will have no effect on the patient's routine treatment. The person obtaining consent will inform the patient that there is no obligation to participate in the study, and will provide his/her name and phone number where he/she can be reached if they have further questions or wish to withdraw from the study at any time. The person obtaining the consent will also provide the patient with a copy of the consent forms and provide ample time for the patient and family to have questions answered prior to enrollment. Copies of the signed consent forms will be given to the patient, and this fact will be documented in the patient's record.

**7.4. Protections Against Risk.** Under the auspices of the Vanderbilt Institutional Review Board, all participants will be protected by the project's staff strict adherence to study protocols governing participant safety, data privacy, informed consent, withdrawal from the study without prejudice, and immediate reporting directly to the PI and the IRB of any adverse events involving the participants. Data obtained with subject identifiers will be kept in password protected electronic files on a VUMC server. All subjects will be assigned a unique study number for use in the REDcap database and all electronic data will be kept in password-protected files to ensure confidentiality. Participants will continue to have access to their usual sources of medical care throughout the study. These measures will provide a very high level of protection against risk to the participants.

**7.5. Potential Benefits of the Proposed Research to Human Subjects and Others.** All participants will gain additional assistance through the one-on-one or group telehealth mindfulness intervention in managing their pain and disability and we anticipate that patients in the study will report improvements in pain interference, function, and psychological well-being. There may also be a potential benefit derived from being enrolled in an investigation and having additional patient assessments. Such additional assessments may detect unrecognized clinical and health issues, which could be of benefit to patients' outcomes. Finally, participants may derive a great deal of personal comfort in knowing that their psychological distress are part of the surgical recovery process. Thus, a potential benefit may be a reduction in stress and anxiety over recovery. The potential for direct patient benefit outweighs any minimal risk of harm to the participants.

**7.6. Importance of the Knowledge to be Gained.** The proposed study is intended to provide new knowledge about the feasibility, acceptability, potential effects, and optimal approach to providing a behavioral intervention to a post-surgical population. Such knowledge is important because the

## Post-op Telehealth Mindfulness Protocol for Spinal Surgery

population of surgical spine patients is growing rapidly, the current treatment regimen appears insufficient based on outcome variability, and there are few other promising therapeutics alternatives for dealing with postoperative recovery.

**7.7. Patient Confidentiality.** All study forms, reports, and other records that are part of the study data collection materials will be identified by coded number to maintain patient confidentiality. All electronic records of study data will be identified by coded number. Clinical information will not be released without written permission of the patient, except as necessary for monitoring by the IRB. Consent procedures and forms, and the communication, transmission and storage of patient data will comply with IRB requirements for compliance with The Health Insurance Portability and Accountability Act (HIPPA).

### Detailed Protocol

Version 7; November 22, 2021

